9.3.3 Removal of Subjects From Therapy or Assessment

The investigator may discontinue treating a subject with study treatment or withdraw the subject from the study at any time for safety or administrative reasons. The subject may decide to discontinue study treatment or withdraw from the study at any time for any reason. The reason for discontinuation will be documented. After discontinuation from study treatment and completing off-treatment visit, subjects will be followed up at least 4 weeks later (ie, greater than or equal to 28 days after last dose but no more than 1 year) unless they withdraw consent. The investigator should confirm whether a subject will withdraw from study treatment but agree to continue protocol-specified, off-treatment study visits, procedures or whether the subject will withdraw consent. If a subject withdraws consent, the date will be documented in the source documents. The Discontinuation From Treatment CRF page will be completed indicating the primary reason(s) for discontinuation. In addition, the date of last dose of study drug(s) will be recorded on the Study Drug Dosing CRF page. Before a subject is withdrawn from study medication due to AE, the possibility of continuing on a single agent should be considered. In the event of an adverse event which leads to treatment interruption or delay of either study drug. The subject may continue treatment with the other study drug as long as there is a clinical benefit for up to 1 year, from start of study treatment, after which any continued treatment would need to be discussed with the Sponsor.

During the Follow-Up Period, subjects who have discontinued study treatment without objective disease progression should have tumor assessments performed according to the

Schedule of Assessments from the date of the last assessment until disease progression is documented or another anticancer therapy is initiated, whichever occurs first, unless the study is terminated or the subject withdraws consent for follow-up.

9.4 Treatments

9.4.1 Treatments Administered

Administration of eribulin mesilate by IV infusion on Days 1 and 8 of a 21-day cycle in combination with irinotecan hydrochloride administered by IV infusion on either Days 1-5 of a 21-day cycle (Schedule A), or Days 1 and 8 of a 21-day cycle (Schedule B).

Irinotecan will be administered first (on days where both treatments are due to be administered), as a 30-minute infusion, followed by eribulin as a 2-5 minute bolus infusion. Eribulin may be diluted in up to 100 mL 0.9% sodium chloride and administered as an IV infusion over 15 minutes (maximum infusion duration), where clinically appropriate.

As long as the subject is still receiving clinical benefit and has not experienced intolerable toxicity, he or she can continue to receive study treatment for up to 1 year, from start of study treatment, after which any continued treatment would need to be discussed with the Sponsor.

In the event of an adverse event which leads to treatment interruption or delay of either study drug, the subject may continue treatment with the other study drug, as long as there is a clinical benefit for up to 1 year, from start of study treatment after which any continued treatment would need to be discussed with the Sponsor.

Phase 1

The dosing schedules being evaluated for Phase 1 will be as follows:

Schedule A

Eribulin mesilate on Day 1 and Day 8 of a 21 day cycle (Starting dose determined by COG protocol ADVL1314/Eisai Study E7389-A001-113).

Irinotecan hydrochloride on Days 1-5 of a 21-Day cycle.

Dose Level	Eribulin mesilate (mg/m ²)	Irinotecan hydrochloride (mg/m ²)
-2	0.8	20
-1	1.1	20
0*	1.4	20
1	1.4	40

*Dose level 0 refers to the starting dose.

Dose level -2 is a further dose reduction in Schedule A for subjects <12 months only.

Schedule B

Eribulin mesilate and irinotecan hydrochloride on Day 1 and Day 8 of a 21-day cycle.

Dose Level	Eribulin mesilate (mg/m ²)	Irinotecan hydrochloride (mg/m ²)
-1	1.1	100
0*	1.4	100
1	1.4	125

*Dose level 0 refers to the starting dose.

Subjects will be allocated in an alternate fashion to either Schedule A or Schedule B, ie, every other subject will be allocated to Schedule A, by the Sponsor until an MTD is reached. If 1 schedule halts or pauses enrollment subjects will be enrolled on the other schedule provided it is open for accrual.

Subjects <12 months will be enrolled on to Schedule A only and at 1 dose level behind \geq 12 months subjects in order to maximize safety for infant subjects. These subjects are included for descriptive purposes only and will not contribute to the determination of the MTD/RP2D for this study, or to the sample size.

Dose Escalation

The traditional 3+3 design will be used for the conduct of Phase 1 of this study.

For both schedules A and B, 3 subjects will be entered into each dose level. The first subject at each dose level must complete the Day 8 assessments before further subjects can be entered at the same dose level. All 3 subjects in the cohort will be followed for a full cycle before the next dose level opens. If 1 subject experiences a DLT, the cohort will need to be expanded to 6 subjects on the same dose level.

If no DLT is observed in a dose cohort, then the dose can be escalated and 3 subjects can be enrolled onto the next dose level. The MTD is defined as the highest dose level at which fewer than 1/3 of subjects experience a DLT during Cycle 1 of therapy.

If, at dose level 0, there are 2 or more subjects with a DLT out of 3 subjects (or 2 DLTs out of 6 subjects after expansion) in Cycle 1, the MTD will have been exceeded and the dose will be deescalated to dose level -1, and the next 3 subjects will be enrolled onto this lower dose level.

The MTD will be determined based on the incidence of DLTs in Cycle 1 of each dose level. Subjects who do not complete Cycle 1 for any reason other than toxicity, ie, DLT, will be

replaced in that cohort in order to complete the number necessary (up to 6) to assess the safety of the dose level cohort.

Toxicities subsequent to Cycle 1 will also be reviewed, but will not count towards determination of dose escalation and MTD/RP2D. If protocol-defined DLTs are observed in a subject after the first cycle at any dose level, the dose will be reduced to the next lower dose level for subsequent cycles.

DLTs are defined as any of the following using the National Cancer Institute Common Terminology Criteria for Adverse Events (CTCAE Version 5.0) during Cycle 1:

Hematological:

1. Neutropenia Grade 4 that lasts >7 days
2. Thrombocytopenia Grade 4 on 2 separate days, or requiring a platelet transfusion on 2 separate days, within a 7-day period
3. Thrombocytopenia Grade 3 complicated by bleeding or requiring platelet or blood transfusion
4. Neutropenia Grade 3 or 4 complicated by fever and/or infection (ANC $<1.0 \times 10^9/L$, fever $\geq 38.0^{\circ}C$)
5. Myelosuppression that causes a delay of >14 days between treatment cycles

Grade 4 neutropenia or platelets $<75,000/mm^3$ on Day 8 that does not resolve to ANC $\geq 750/mm^3$ and platelets $\geq 75,000/mm^3$ (transfusion independent) by Day 11 will be considered dose-limiting

Non-hematological:

1. Grade 3 or 4 non-hematological toxicities related to study drug **except for**:
 - inadequately treated nausea and/or vomiting,
 - Grade 3 liver enzyme elevation (including ALT/AST),
 - Grade 3 fever or Grade 3 infection,
 - Grade 3 hypophosphatemia, hypokalemia, hypocalcemia or hypomagnesemia responsive to oral supplementation
2. Grade 3 or above diarrhea despite adequate treatment
3. Non-hematological toxicity that causes a delay of ≥ 14 days between treatment cycles
4. Day 8 dose omission or interruption for more than 2 weeks due to non-recovery of any toxicity related to the study drug
5. For subjects <12 months (at the time of DLT), any \geq Grade 2 drug-related non-hematological toxicity
6. **DLT exception:** Allergic reactions that lead to discontinuation of study drug during Cycle 1

Accrual will be suspended when a cohort of 3 has enrolled with pending toxicity data or when the MTD/RP2D for the combination has been met. If, following de-escalation from

dose level 0 (to dose level-1), 2 DLTs are observed, that dose and schedule will be declared too toxic for further evaluation. For subjects <12 months, if following de-escalation from dose level -1 (to dose level -2 on Schedule A), 2 DLTs are observed, that dose and schedule will be declared too toxic for further evaluation. Subjects <12 months are included for descriptive purposes only and will not contribute to the determination of the MTD/RP2D for this study. Up to 36 pediatric subjects (18 subjects per schedule) who meet all the inclusion criteria and none of the exclusion criteria, will be enrolled in Phase 1.

MTDs will be obtained for both Schedule A and Schedule B and the most appropriate schedule will be taken forward to Phase 2 and will represent the RP2D (See Section [9.4.4](#) for details on schedule selection).

If a large number of dose modifications are observed after completion of cycle 1 (eg, intolerable Grade 2 toxicities), the sponsor will discuss with investigators whether a lower dose level than the MTD should be carried forward as the RP2D for this study.

Criteria for Dosing Modifications

Dose reduction and interruption for eribulin mesilate and irinotecan hydrochloride-related toxicity will be performed according to the following instructions:

Treatment will not be administered if any of the following values are recorded ([Table 7](#)).

Table 7 Criteria for Administration of Study Medication	
a): Do not administer Cycle 1 Day 1 treatment where:	
Absolute Neutrophil Count	<1.0 × 10 ⁹ /L or 1,000/mm ³
Platelets	<100 × 10 ⁹ /L or 100,000/mm ³
Non-hematological toxicity	Any >Grade 2 except for inadequately treated nausea and/or vomiting.
Gastrointestinal toxicity	Bowel function deteriorated since pre-treatment/baseline and requires antidiarrheal medications for within 24 hours before the next chemotherapy administration.
b): Do not administer any Day 8 treatment where:	
Absolute Neutrophil Count	<0.75 × 10 ⁹ /L or 750/mm ³
Platelets	<75 × 10 ⁹ /L or 75,000/mm ³
Non-hematological toxicity	Any >Grade 2 except for inadequately treated nausea and/or vomiting.
Gastrointestinal toxicity	Bowel function deteriorated since pre-treatment/baseline and requires antidiarrheal

	medications for within 24 hours before the next administration of irinotecan hydrochloride.
c): Do not administer any subsequent Day 1 treatment where:	
Absolute Neutrophil Count	$<1.0 \times 10^9/L$ or $1,000/mm^3$
Platelets	$<75 \times 10^9/L$ or $75,000/mm^3$
Non-hematological toxicity	Any >Grade 2 except for inadequately treated nausea and/or vomiting.
Gastrointestinal toxicity	Bowel function deteriorated since pre-treatment/baseline and requires antidiarrheal medications for within 24 hours before the next chemotherapy administration.

If the dose cannot be administered as planned due to treatment-related toxicity, the dose should be delayed according to the following instructions.

Day 1 of each cycle: If treatment cannot be administered on Day 1, the dosing should be delayed until recovery to above these values ([Table 7a](#) Cycle 1 & c subsequent cycles). The Day 1 dose will be rescheduled for when the criteria for treatment administration are met. The dose level may have to be reduced following a dose delay in accordance to the instructions for dose reduction ([Table 8](#)).

Day 8 of each cycle: If treatment cannot be administered on Day 8, the dosing should be delayed until recovery to above these values ([Table 7b](#)) as follows:

Hematological toxicity:

- Subjects who have Grade 4 neutropenia or platelets $<75,000/mm^3$ on Day 8 will have their dose withheld. If the toxicity resolves to ANC $\geq 750/mm^3$ and platelets $\geq 75,000/mm^3$ (transfusion independent) by Day 11, the dose may be given. If the toxicity does not resolve to ANC $\geq 750/mm^3$ and platelets $\geq 75,000/mm^3$ by Day 11, the dose will be omitted and this will be considered a DLT. Subjects should receive subsequent cycles of drug but at the next lower dose level ([Table 10](#)). Subjects who require that their Day 8 dose be omitted for Grade 4 neutropenia or platelets $<75,000/mm^3$ after two dose reductions must be removed from protocol therapy.
- Subjects who meet hematological DLT criteria on Day 8 will have their Day 8 dose omitted. Subjects should receive subsequent cycles of drug but at the next lower dose level. Subjects who require that their Day 8 dose be omitted for hematologic DLT after two dose reductions must be removed from protocol therapy.

Non-hematological toxicity:

- Subjects who have Grade 3 or Grade 4 non-hematological toxicity attributable to the study drug prior to the Day 8 dose (with the exception of the DLT exclusions) will be

considered to have had a DLT. If the toxicity resolves to meet eligibility or \leq Grade 2 (if not part of eligibility criteria) by Day 8, the dose may be given but at the next lower dose level.

- Subjects who have Grade 3 or Grade 4 non-hematological toxicity attributable to the study drug on Day 8 prior to dosing (with the exception of the DLT exclusions) will have their dose withheld and this will be considered a DLT. If the toxicity resolves to meet eligibility or \leq Grade 2 (if not part of eligibility criteria) by Day 11, the dose may be given but at the next lower dose level. If the toxicity does not resolve by Day 11, the dose will be omitted. Subjects should receive subsequent cycles of drug but with dose modifications ([Table 10](#)).
- For subjects <12 months any \geq Grade 2 non-hematological toxicity attributable to study drug prior to the Day 8 dose will have their dose omitted. Subjects should receive subsequent cycles of drug at the next lower dose level ([Table 10](#)).
- Subjects who have a dose-limiting hematological or non-hematological toxicity that does not resolve to meet eligibility or baseline parameters within 21 days after the planned start of the next treatment cycle must be removed from protocol therapy.

For Schedule A, irinotecan doses days 2-5 can be delayed up to cycle Day 10 (of a 21 day cycle), at the discretion of the Investigator and as long as the subject meets the criteria for administration of study medication for Day 8 as detailed in [Table 7](#). If the subject does not meet the Day 8 criteria for administration by cycle Day 10 then dosing should not occur until the next cycle and as long as the subject meets the subsequent Day 1 dosing criteria for administration ([Table 8](#)).

Please note, use of hematopoietic growth factor support is not permitted in Cycle 1 and is only permitted in subsequent cycles as per institutional guidelines. Subjects known to have reduced UGT1A1 activity will be monitored carefully for hematological toxicity.

The treatment will be permanently reduced to the next lowest dose level ([Table 10](#)) after the occurrence of the following events

Table 8 Criteria for Reduction of Study Medication to the Next Lowest Dose Level

Absolute Neutrophil Count	Grade 4 neutropenia >7 days Grade 3 or 4 febrile neutropenia and/or infection requiring treatment with antibiotics and/or growth factors
----------------------------------	---

Platelets	Grade 4 thrombocytopenia Grade 3 thrombocytopenia requiring platelet or blood transfusion or both
Non-hematological toxicity	Grade 3 or 4 toxicities (attributable to study drug); except Grade 3 hypophosphatemia, hypokalemia, hypocalcemia or hypomagnesemia that respond to supplementation For subjects <12 months any \geq Grade 2 non-hematological toxicity attributable to study drug prior to the Day 8 dose will have their dose omitted and this will be considered a DLT. Subjects should receive subsequent cycles of drug but with dose modifications as per Table 10
Gastrointestinal toxicity	\geq Grade 3 or intolerable Grade 2 diarrhea For subjects on dose levels 0 and -1 dose reductions of 20% of the current irinotecan dose should be made. If there are 2 or more diarrhea DLTs on these dose levels, the irinotecan dose levels will be re-evaluated by the Sponsor, and an appropriate lower dose level will be agreed with the investigator. If the diarrhea toxicity does not recover following a dose reduction of 20% (of dose level 0 or -1), treatment should be discontinued

If hematological or non-hematological toxicities do not recover following a dose reduction to dose level -1 (dose-level -2 for subjects <12 months) and the use of hematopoietic growth factors, for hematological toxicities, the subject will discontinue treatment (except for cases of irinotecan related diarrhea, see below). However, if the subject is deemed to have clinical benefit, continuation of treatment may be discussed with the sponsor.

To ensure safety for subjects, the study drug must be discontinued in the cases outlined in [Table 9](#).

If, in the opinion of the Investigator, a dose reduction as per the criteria noted in [Table 8](#) is not necessary, due to adequate supportive care and use of prophylaxis (eg, growth factor support) to prevent recurrences, each individual case should be discussed with and agreed by the Sponsor.

Table 9 Criteria for Discontinuation of Study Medication

ALT $>3 \times$ ULN and total bilirubin $>2 \times$ ULN

ALT >8 × ULN at any time, regardless of total bilirubin or accompanying symptoms
ALT >5 × ULN for 2 or more weeks, regardless of total bilirubin or accompanying symptoms
ALT >3 × ULN, accompanied by symptoms consistent with hepatic injury (fatigue, nausea, vomiting, right upper quadrant pain or tenderness, fever, or rash). Clinical judgement should be used based on the combination of the laboratory LFT results and clinical symptoms. Additionally, in subjects with liver metastases with pre-existing ALT >3 x ULN at study baseline, any additional increase in ALT values from baseline and clinical symptoms consistent with a syndrome of hepatic injury as described above should be considered for further assessment and drug discontinuation. Clinical symptoms alone consistent with deterioration of liver function should lead to additional laboratory assessments and evaluation of potential study drug related liver toxicity.

Instructions for QTc prolongation on electrocardiogram (ECG):

Increase the frequency of ECG and electrolyte monitoring in subjects who: develop Grade 2 QTc prolongation, are receiving agents that are known to prolong QTc interval, or have clinically relevant electrolyte abnormalities. Permanently discontinue study treatment in subjects who develop \geq Grade 3 QTc prolongation, and monitor ECGs and electrolytes more frequently in consultation with cardiologist advice and in line with local practice until the QTc interval returns to baseline.

Table 10 Study Medication Dose Levels by Schedule for Phase 1

Dose Level	Eribulin mesilate (mg/m ²)	Irinotecan hydrochloride (mg/m ²)
Schedule A		
-2	0.8	20
-1	1.1	20
0	1.4	20
1	1.4	40
Schedule B		
-1	1.1	100
0	1.4	100
1	1.4	125

Dose level -2 is a further dose reduction in Schedule A for subjects <12 months only.

Do not re-escalate dose level after the dose level has been reduced.

Phase 2

As per protocol amendment #5, the data from the Phase 1 portion of this study showed that there was a tolerable safety profile in both schedules, with similar PK profiles; however, 2 PRs were noted in Schedule A, one of which was confirmed. Following discussions with the investigators and independent experts, based upon the similar toxicity and PK profiles and taking into account the 2 PRs noted in Schedule A, Schedule A Dose Level 1 (eribulin 1.4

mg/m² D1 and D8 with irinotecan 40 mg/m² D1 – D5 of a 21- day cycle) from Phase 1 was selected as the RP2D for the Phase 2 portion of this study for subjects \geq 12 months of age.

As per Amendment 6, subjects aged >6 months and <12 months will be enrolled to Schedule A with a modified dose of eribulin Dose Level -2 (0.8 mg/m² D1 and D8) with the irinotecan dose maintained Dose Level 1 (40 mg/m² D1 – D5) of a 21-day cycle.

A modified dose of eribulin with the irinotecan dose maintained is being used for subjects <12 months in order to maximize safety for infant subjects. The modified dose of eribulin is aligned with the Children's Cancer and Leukaemia Group ([CCLG](#)) ([Chemotherapy Standardization Group 2008](#)) guidance on pediatric dosing where a dose has not been established.

The dose levels as per [Table 11](#) should be used in the Phase 2 portion of the study when following the criteria for dose reductions ([Table 8](#)), the agent most likely to be the cause of toxicity (eg, irinotecan for diarrhea, eribulin for neuropathy or neutropenia) should be reduced by one dose level if these criteria are met. If in the investigator's opinion both agents should be reduced this may be permitted after discussion with the Sponsor.

Table 11 Schedule A Dose Levels for Phase 2	
Dose Level	Eribulin mesilate (mg/m²)
Eribulin – Days 1 & 8	
-4	0.4
-3	0.6
-2**	0.8
-1	1.1
1*	1.4
Irinotecan hydrochloride (mg/m²) – Days 1-5	
-2	20
-1	30
1*	40

For subjects \geq 12 month to \leq 25 years of age:

* Dose level 1 eribulin (1.4 mg/m² Days 1 and 8) and irinotecan (40 mg/m² Days 1 – 5).

For subjects >6 months and <12 months of age:

**Dose level -2 for eribulin (0.8 mg/m² Days 1 and 8) and Dose level 1 for irinotecan (40 mg/m² Days 1 – 5) is maintained.

[figure not shown]
Do not re-escalate dose level after the dose level has been reduced. If toxicities do not recover after 2 dose reductions, treatment with that agent must be discontinued.

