- j. Hematology lab tests will be performed weekly for subjects aged ≥ 12 months and twice weekly for subjects < 12 months; a complete blood count can be performed at a local laboratory when the subject is not attending the investigator site for dosing or other study visits.
- k. Albumin, calcium, magnesium, cholesterol, lactate dehydrogenase, phosphorus, total protein, triglycerides, and uric acid are all to be assessed at baseline. Cholesterol, triglycerides and uric acid are not required for assessment at subsequent chemistry measurement time points.
- l. Eribulin will be administered on Day 1 and Day 8 of a 21-day cycle together with irinotecan either on Schedule A (Days 1-5) or Schedule B (Day 1 and Day 8) of a 21-day cycle, depending on which schedule is found to be most appropriate for Phase 2. As per protocol amendment #5, Schedule A Dose Level 1 was selected as the RP2D for the Phase 2 portion of this study.
- m. PK sample collection schedule:
 - Phase 2 (Cycle 1):** Eribulin assay only:
Cycle 1, Day 1 (at the end of the infusion, 0.5 to 6 hours and 24 to 120 hours after eribulin infusion) and on Cycle 1, Day 8 (pre-dose of eribulin and at the end of the infusion). Subjects who weigh < 6 kg will not have PK samples taken.
 - n. 12-lead ECG will be obtained pre-infusion (after irinotecan administration and prior to eribulin infusion on the days when administered together) and post-infusion on Day 1 and Day 8 of Cycle 1 and as clinically indicated during subsequent cycles and during follow-up (28 days after the last dose of drug).
 - o. If urine protein is $\geq 2+$ on urinalysis, a 24 hour urine test should be performed.
 - p. **Pre-study phase:** Screening tumor assessments using CT of the chest/abdomen/pelvis and other areas of known disease or newly suspected disease should be performed between Day -28 and Day -1.

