9.7.1.8 Safety Analyses

The primary endpoint for Phase 1, i.e., the incidence of DLTs will be summarized by dose level for the DES using frequency and percentage.

Additionally, toxicity in Phase 2 for the Safety Analysis Set will be monitored on an ongoing basis. If the number of AEs that would have qualified as DLTs on the Phase 1 portion exceeds 1/3, a meeting with the investigators will be convened to determine if the dose should be lowered. The rule of one-third (1/3) will be applied to the number of subjects in an increment of 3 subjects at the same dose level (eg, 3, 6, 9 subjects). Likewise, if ongoing moderate toxicities develop into “intolerable Grade 2” events, the recommended Phase 2 dose may also be re-evaluated in consultation with the protocol investigators.

All evaluation of safety other than the Phase 1 primary objective in DLT evaluation will be performed on the Safety Analysis Set. Safety data that will be evaluated include adverse events, clinical laboratory results, ECG, and vital signs.

Descriptive summary statistics (mean, standard deviation, median, minimum, maximum) of clinical laboratory test results, vital signs measurements, ECG parameters, and changes from baseline will be presented.

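### The thrombocytopenia DLT criteria behind the Phase 2 one-third toxicity rule count a complicated Grade 3 event but can miss the same complication at Grade 4

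*Protocol*

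**What the plan says.** Protocol 9.4.1 lists the hematological DLTs; the Synopsis and SAP 3.2.1 repeat the two criteria at issue.

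- Criterion 2: "Thrombocytopenia Grade 4 on 2 separate days, or requiring a platelet transfusion on 2 separate days, within a 7-day period".
- Criterion 3: "Thrombocytopenia Grade 3 complicated by bleeding or requiring platelet or blood transfusion".

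The next item in the list names both grades: "Neutropenia Grade 3 or 4 complicated by fever and/or infection". Appendix 1 gives the grades separate platelet ranges: Grade 3 is below 50,000 down to 25,000/mm³, and Grade 4 is below 25,000/mm³.

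Protocol 9.7.1.8 carries the definition into Phase 2. The condition reads "If the number of AEs that would have qualified as DLTs on the Phase 1 portion exceeds 1/3", and the consequence is a meeting with the investigators about lowering the dose. It adds: "The rule of one-third (1/3) will be applied to the number of subjects in an increment of 3 subjects at the same dose level", with 3, 6 and 9 subjects as examples.

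Two further provisions matter. Table 8 (Table 2 in the Synopsis) reduces the dose for Grade 4 thrombocytopenia without conditions, but at the lower grade only for "Grade 3 thrombocytopenia requiring platelet or blood transfusion or both". Table 14, footnote j, sets the blood-count schedule: "Hematology lab tests will be performed weekly for subjects aged" 12 months or more, and twice weekly for infants.

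**The concern.** A toxicity count should not drop an event because the platelet count was lower. Here it can. At Grade 3, any bleeding or one transfusion is enough. At Grade 4, bleeding is not a criterion, and a transfusion counts only if platelets are needed on two separate days within seven. The list writes out both grades for febrile neutropenia, and writes Grade 3 or above for diarrhea, so criterion 3 cannot safely be read as including Grade 4.

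Phase 1 is finished, so the live consequence is the Phase 2 tally, which is the protocol's ongoing numerical check on the recommended dose in children. It could include the milder event and leave out the worse one. The wording also affects how the completed Phase 1 DLT counts are read.

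**Working it through.** **Step 1: apply the two criteria to each pattern.** The inputs are criteria 2 and 3 (9.4.1) and the platelet row of Table 8. Criterion 2 is met if there are at least 2 Grade 4 days, or at least 2 platelet-transfusion days, within 7 days. Criterion 3 is met if the grade is 3 and there is bleeding or at least 1 transfusion. The right-hand column reads criterion 3 as Grade 3 or 4.

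| Pattern | Counted as written | Table 8 dose reduction | Counted if criterion 3 covers Grade 3 or 4 |
|---|---|---|---|
| Grade 3, bleeding only | yes | no | yes |
| Grade 3, one platelet transfusion | yes | yes | yes |
| Grade 3, both | yes | yes | yes |
| Grade 4 on one day, neither | no | yes | no |
| Grade 4 on one day, bleeding only | **no** | yes | yes |
| Grade 4 on one day, one platelet transfusion | **no** | yes | yes |
| Grade 4 on one day, both | **no** | yes | yes |
| Grade 4 on two days, or two platelet-transfusion days | yes | yes | yes |

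Three patterns are inverted. The amended reading corrects those three and changes no other.

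**Step 2: look for another route to a DLT (9.4.1).** A one-day Grade 4 event of this kind still counts if any of these applies:

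- Day 8 platelets below 75,000/mm³ have not recovered by Day 11.
- The Day 8 dose is omitted because a drug-related toxicity has not recovered.
- Myelosuppression delays the next cycle by more than 14 days.
- The bleed is itself a related Grade 3 or 4 event.
- The subject is under 12 months and has a related non-hematological event of Grade 2 or higher.
- A separate Grade 3 count has its own bleeding or transfusion.

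Take a child aged 12 months or more with platelets of 20 x10^9/L on Day 15, a nosebleed below Grade 3 and one transfusion, who recovers without a long delay and has no separate qualifying Grade 3 count. No route applies. At 40 x10^9/L, criterion 3 is met.

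**Step 3: can the two-day limb be observed?** Weekly counts fall nominally on Days 1, 8, 15 and 22. Any 7 consecutive calendar days then contain one scheduled count. The two-day Grade 4 limb therefore usually needs an unscheduled repeat, although the ±3-day visit window can bring two counts closer together.

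**Step 4: effect on the trigger.** The proportion must exceed 1/3, so at least 2 of 3, 3 of 6 or 4 of 9 is needed. One child moves 1/3 (33.3%) to 2/3 (66.7%), 2/6 (33.3%) to 3/6 (50.0%), or 3/9 (33.3%) to 4/9 (44.4%).

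The plan states no operating characteristic for this rule and no event frequency, so there is no figure to reproduce and the rates below are assumptions. Let p be the chance that a subject has a counted event, with subjects independent and at most one event tallied per subject. For p = 0.20, a group of 3 has 0, 1, 2 or 3 events with probability 0.512, 0.384, 0.096 and 0.008, so P(2 or more) = 0.104.

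- Look at 3: trigger probability is 0.104. Otherwise continue with 0 events (0.512) or 1 event (0.384).
- Look at 6, total of 3 or more: 0.512 × 0.008 + 0.384 × 0.104 = 0.0440. The probabilities of continuing with 1 and 2 events are 2 × 0.512 × 0.384 = 0.3932 and 0.512 × 0.096 + 0.384² = 0.1966.
- Look at 9, total of 4 or more: 0.3932 × 0.008 + 0.1966 × 0.104 = 0.0236.
- Sum: 0.104 + 0.0440 + 0.0236 = 0.1716, or 17.2%.

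The same calculation for other rates gives:

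| Subjects with only an uncounted event (assumed) | p if counted | P(trigger by subject 9) |
|---|---|---|
| 0% (as written) | 0.200 | 17.2% |
| 0.5% | 0.205 | 18.1% |
| 1% | 0.210 | 19.0% |
| 2% | 0.220 | 20.9% |
| 5% | 0.250 | 27.1% |

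**The case against.** The strongest reply is that the gap is narrow and its consequence mild. Six other routes catch many of these events. The Day 8 route may catch more than it first appears to: recovery by Day 11 must be transfusion independent, and the eligibility criteria define that as no platelet transfusion within 7 days. If that definition carries over, a child transfused after a Day 8 Grade 4 count cannot qualify as recovered by Day 11. What remains is mainly a short nadir later in the cycle. Thrombocytopenia is also not the expected limiting toxicity: the Introduction gives neutropenia for eribulin in children, and 9.2 gives gastrointestinal toxicity for daily irinotecan. The rule only calls a meeting, tolerability is also assessed at each futility analysis, and Table 8 already reduces the dose. All of this stands. It limits the practical effect but does not put the criteria in the right order.

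The assumed rates are a fair target as well. With only 0.5% to 1% of subjects affected, the trigger probability rises to 18.1% to 19.0%, a small change. The inversion does not depend on any rate.

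Two objections concern the remedy. Amendment 03 describes Phase 2 monitoring as using the Phase 1 rule, and a wider criterion departs from the definition under which the dose was chosen. That is a real cost, though a small one if stated openly. The change would also override criterion 2's two-day transfusion requirement at Grade 4. That is true but unavoidable: adding bleeding alone would leave one transfusion counting at Grade 3 and not at Grade 4.

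**Conclusion.** The concern holds. As written, criteria 2 and 3 put three one-day Grade 4 patterns (bleeding, one platelet transfusion, or both) below their Grade 3 counterparts, and 9.7.1.8 takes that ordering into the Phase 2 tally. This rests on the text alone, reading Grade 3 in criterion 3 literally, as the neighbouring items support. If the sponsor means Grade 3 or worse, the text should say so.

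The practical size cannot be determined from the documents. A missed event matters when the tally stands at exactly one-third. Under an assumed 20% counted rate, the chance of triggering by nine subjects would rise from 17.2% to between 18.1% and 27.1% as the assumed uncounted share runs from 0.5% to 5%. The response-rate analysis and the Simon boundaries are unaffected, and individual dosing is protected. The correction is worth making because it is cheap and the rule concerns children's safety, but it is not critical to the trial.

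**What to change.** In Protocol 9.7.1.8 and the matching Synopsis paragraph, add one sentence stating that, for the Phase 2 one-third tally, hematological criterion 3 applies to thrombocytopenia of Grade 3 or 4, with its bleeding and transfusion conditions unchanged. The sentence can note that the completed Phase 1 DLT counts stand as adjudicated.

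The cost is a few words, a slightly higher count of DLT-type events, perhaps an extra meeting, and a small declared difference from the Phase 1 definition. No Phase 1 re-adjudication and no change to sample size or endpoints is needed. The SAP does not describe the Phase 2 tally, so no planned analysis changes.
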